#### Adverse events and concomitant medication dates

If the start date of an AE is incomplete, a full start date will be imputed following a ‘worst case’ logic favouring treatment emergency and length of AE duration. If the incomplete start date is unambiguously before date of first vaccination, the latest possible date compatible with the partial date, but before first vaccination, will be chosen. Otherwise, the earliest possible date compatible with the partial date, but after date of first vaccination will be chosen. So, for example:

Completely missing start date:

- the AE will be considered as concomitant/treatment emergent with the start date imputed as treatment start date.

If Month is missing:

- If the incomplete date is in the same year as day of first dosing, assign the treatment start date as the AE/medication start date.
- If this is not the case, assign January as the month and the 1.th of January as day/month if AE/medication day is also missing.

If Year is missing:

- Impute the year of first vaccination. If the imputed date is then after first vaccination date then retain it. Otherwise impute the date of first vaccination.

## 4.3 Subject Disposition

All randomised subjects will be accounted for. All post-randomisation discontinuations will be summarised by reason for discontinuation. The number and characteristics of subjects screened but not found eligible will be stated in the clinical study report, together with a summary of reasons and types of failures. A detailed listing of these subjects will be provided.

The number of subjects in each analysis set as defined below will be summarised with frequency and percentage in a subject disposition table.

## 4.4 Demographics, baseline characteristics and concomitant medications

### 4.4.1 Demographics data and medical history

Demographic data for mothers contain age at delivery, race, weight, height, BMI, gestational age at randomization. Demographic data for babies: height, weight, gestational age, and gender. Tabulations of these data are performed by treatment group.

- Medical history and concomitant illness will be summarised by SOC and PT for MedDRA version 23.1 or later. The table will display the total number of subjects with medical history, the percentage of subjects (%) with a reported medical history and the number of illnesses reported and will be presented by SOC sorted alphabetically and PT sorted in decreasing frequency of occurrence.
- Prior and concomitant medication will be tabulated separately and summarized by WHO Drug Dictionary terms (version WHODRUG Global C3 September 1, 2020, or later). The table will display the total number of subjects with medication, the percentage of subjects (%) with medication and the number of medications and will be presented by ATC level 4 sorted alphabetically and preferred names sorted in decreasing frequency of occurrence. Prior and concomitant medications are defined as follows:
  - Prior medication: Any medication episode initiated prior to the start of treatment (IMP)
  - Concomitant medication: Any medication episode initiated during the treatment period
- Viral serology – eligibility data regarding Human Immunodeficiency Viruses (HIV) and hepatitis B and C

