#### 4.3.2 Description of individual study visits

##### VISITS FOR MOTHERS:

###### Screening, Day -14 to Day -1: Eligibility assessment:

Obtain informed consent, check eligibility against the in/exclusion criteria, obtain and record demography, medical and obstetric history, current medication (including supplements and over the counter preparations), conduct a full physical examination (respiratory, cardiovascular, gastrointestinal, gross central nervous system, gross musculoskeletal) by a physician, obstetric examination\* (fundal height, foetal movement and foetal heart rate), measure and record height and weight (for calculation of BMI), vital signs (heart rate, blood pressure, oral temperature). Collect samples for urinalysis, safety laboratory tests (haematology and serum biochemistry), determination of subject's Hep B, Hep C, HIV and syphilis status (assessment based on results from last samples taken in first trimester, if available, otherwise samples are taken at the screening visit), record result of the last ultrasound for the assessment of the subject's eligibility for inclusion in the study. Subjects will be contacted by phone and informed if they are eligible to proceed from screening, and, if eligible, to confirm the appointment for Visit 1, Day 0, where they will be randomised and assigned to one of the Groups 1 to 5, see Table 1.

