### 5.10.1 Recording of previous and concomitant medications and vaccines

Prior and concomitant medications (CMs) or vaccines are to be recorded in the eCRF including over-the-counter medications and supplements.

Concomitant medication is any medication or vaccine apart from the investigational vaccine and placebo that the subject receives while participating in the study. The investigator or delegate must seek information on CM use, as specified for the individual study visits as per Table 2 and Table 3. The information collected for CM must include:

- Medication name (preferably generic name)
- Indication
- Dosage
- Frequency
- Route of administration
- Start and stop date or ongoing

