## 7 Deviations from protocol

- An exploratory analysis of weight of infant over time is added.
- Adverse events in babies are added as secondary safety endpoint(s).
- Central monitoring is described in some detail, but no specific analysis of monitoring data is defined.

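### The SAP splits prior from concomitant medication by start date alone, so drugs already in use at the first injection and continued afterwards are missing from the concomitant medication table.

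*SAP*

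**What the plan says.** SAP 4.4.1 gives two definitions, both resting on when an episode began:

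- "Prior medication: Any medication episode initiated prior to the start of treatment (IMP"), with no condition on when it stopped;
- "Concomitant medication: Any medication episode initiated during the treatment period".

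The same section says that "Prior and concomitant medication will be tabulated separately". It has no class for drugs begun earlier and continued, and the SAP does not say when the treatment period ends.

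Protocol 5.10.1 uses receipt, not start date: "Concomitant medication is any medication or vaccine apart from the investigational vaccine and placebo that the subject receives while participating in the study". Among the items to record for each medication it lists "Start and stop date or ongoing". At screening, Protocol 4.3.2 has sites record "current medication (including supplements and over the counter preparations"), so drugs in use at entry will be in the database.

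Protocol 7.7 plans to compare the arms on prior and concomitant medication. SAP section 7, which lists the SAP's departures from the protocol, has three entries: the infant weight analysis ("An exploratory analysis of weight of infant over time is added"), adverse events in babies, and central monitoring. The medication definition is not among them.

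**The concern.** A concomitant medication table is read as a summary of what participants were taking while they were exposed to the study product. Under the SAP wording it shows only what was newly started. A woman on an inhaled steroid or a supplement from early pregnancy to delivery would not appear in it.

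The prior table does not fill the gap. It puts a course that ended before the first injection in the same class as a drug taken throughout dosing. From the two tables together, a reader cannot tell how many women in each arm used a given background drug while the antibody response was forming or while reactogenicity was being recorded. At stake is whether the descriptive comparison promised in Protocol 7.7 shows what its title implies.

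**Working it through.** The plan states no figure for medication use, so there is none to reproduce. The check applies both definitions to every possible timing of an episode.

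| Timing of the episode | SAP 4.4.1 | Protocol 5.10.1 | Agree? |
|---|---|---|---|
| 1. Started and stopped before consent | Prior | Not concomitant | Yes |
| 2. Stopped between consent and first injection | Prior | Concomitant | No |
| 3. Started before first injection, still taken after it | Prior only | Concomitant | No |
| 4. Started during the treatment period | Concomitant | Concomitant | Yes |
| 5. Started after the treatment period, before Visit 11 | Neither, if the period ends earlier | Concomitant | Cannot be settled |

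**Row 3** is the point. For any one drug and arm, let A be the set of women with a row 3 episode and B the set with a row 4 episode. The SAP table counts B. A table of use during treatment would count A or B. The shortfall is the number of women in A but not in B. It cannot be negative, so for completely dated records the direction is understatement. Its size depends on how common ongoing use is, which neither document states.

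**Row 2** is a smaller difference. It covers drugs stopped in the screening window (Day -14 to Day -1) or otherwise between consent and first injection. Treating these as prior is a sensible analysis convention, but it still differs from the protocol and should be declared.

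**Row 5** depends on a term left open. The schedules in both documents use one combined heading for treatment and follow-up. If the period runs to Visit 11, row 5 is empty. If it ends at the last injection, products first given between then and delivery, such as intrapartum antibiotics, fall in neither table. The documents do not say which reading applies.

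**Which drugs fall in row 3?** Protocol 4.6.3 excludes women who had systemic steroids in the 6 weeks before the first dose, immunosuppressants, chemotherapy or radiotherapy in the 24 weeks before, blood products or immunoglobulins in the 12 weeks before, or investigational products in the 12 weeks or 5 half-lives before. An eligible woman should not be on these at Visit 1. Row 3 is therefore mainly permitted background therapy.

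**Partial dates.** Under SAP 4.2, when the month is missing and the year is that of first dosing, the instruction is to "assign the treatment start date as the AE/medication start date". That record then counts as concomitant. The same drug with a complete earlier start date is prior only. This pushes in the opposite direction to row 3 and affects incomplete records only.

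**The case against.** The strongest reply is that little depends on this. Ongoing drugs are displayed in the prior table at the same level of detail, and SAP 4.1 says all data will be listed. Protocol 5.10.1 sits in a section on recording and tells sites what to collect; Protocol 7.7 does not prescribe how the classes are split for tabulation. No analysis set, immunogenicity comparison or power calculation uses the split. All of this stands, and it limits the point to descriptive tables. It does not remove it: the protocol offers no other definition of the term, and the prior table cannot recover use during dosing.

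A reader might also infer more than the documents support:

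- *That the rule hides imbalance in systemic steroids, immunosuppressants, immunoglobulins or vaccines.* The pre-dose exclusions keep the listed drugs out at entry, and one begun during dosing is counted as concomitant. A vaccination is a single event and cannot be ongoing. An ineligible user would be a protocol deviation, tracked separately.
- *That more than half of the time to delivery is uncovered.* Taking 18 weeks (126 days) to delivery and a nominal last injection on Day 56, (126 − 56)/126 = 70/126 = 56%. This is a share of calendar days, not of women or medications. It also assumes that the treatment period ends at Visit 5, which neither document states.
- *That most background treatment is left out.* No usage rate is given.
- *That the partial-date rule is a separate error.* SAP 4.2 presents it as a worst-case convention and keeps dates that are clearly before first vaccination where they are. Some difference between complete and incomplete dates comes with any imputation.

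**Conclusion.** The point holds as a definitional error in a descriptive summary. Read literally, SAP 4.4.1 leaves out of the concomitant table every medication with a complete start date before the first injection that continued after it. The protocol counts these as concomitant, and the change is undeclared. The table is understated by an amount the documents do not allow to be computed. This rests on two assumptions: that the SAP definitions will be programmed as written, and that some women enter on continuing therapy. The second is likely, since screening records current medication and the protocol permits inhaled and topical steroids. The immunogenicity results, error rates and sample size are unaffected, and the underlying records remain available.

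**What to change.** Replace the two definitions in SAP 4.4.1 with:

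- *Prior:* stopped before the first IMP injection.
- *Concomitant:* taken on or after the first IMP injection, whatever the start date, including drugs started earlier and ongoing, up to the end of the participant's recording period.

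The last clause also removes the dependence on an undefined end of the treatment period.

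For a partial start date, classify the record by its stop date or ongoing flag. If those are missing too, treat it as concomitant, which keeps the worst-case direction of SAP 4.2.

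In SAP section 7, list the one remaining difference from Protocol 5.10.1: drugs stopped between consent and first injection are tabulated as prior. Record the revision in the change log.

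The cost is two definitions, a short rule for partial dates, one deviation entry and one derivation flag. No new data are needed, because start, stop and ongoing status are already collected.

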#### 4.4.2 Baseline data

With respect to IgG antibody, **for mothers**, baseline data are defined as the non-missing assessment before the first injection of the first IMP.

For general safety assessments (vital signs), baseline is defined as the pre-dose measurement on Day 0 (Visit 1). For laboratory assessments (haematology, chemistry, coagulation, and urinalysis) baseline is defined as the last measurement prior to the first IMP injection.

Change from baseline will be derived for all post-baseline timepoints as the difference between each post-baseline timepoint value and the baseline value. If either baseline or post-baseline values are missing, no change from baseline will be calculated. For variables with positive values, by definition, percent change from baseline will be derived as change from baseline divided by the baseline value and multiplied by 100.

Baseline assessments of physical examination, vital signs, and laboratory measurements will be presented as part of the Safety tables and listings.

#### 4.5 Analysis of immunogenicity (primary endpoint)

The primary objective of the study will be assessed using the following endpoints, based on the cord blood from subjects in the BIG set:

- A) IgG antibody concentrations specific to each of the four chosen AlpN proteins.
- B) Proportion of subjects reaching AlpN-specific IgG concentrations at or above the following cut points: 0.1, 0.2, 0.5, 1, 2, 4 and 8 µg/mL.

The primary immunological endpoints will be defined as the values of the above parameters obtained in cord blood at the time of delivery. According to protocol, a missing or invalid cord blood sample can be replaced by a venous infant blood sample, provided this is taken within 72 hours from delivery.

The GMC and corresponding 95% CI for the IgG antibody concentrations will be estimated, by intervention group, assuming a normal distribution on the log-scale, the anti-log transformation will then be applied before presentation. The proportion of subject reaching the IgG antibody concentrations above the prespecified cut points will be reported by intervention group and 95% confidence intervals will be derived using the Wilson method. Additionally, the endpoints will be compared, as described below, between the 5 intervention groups presented in Table 1.

In terms of interpretation, comparison between groups 1, 2, 3 and 4 will form the main focus, with group 1 as the perceived standard, whereas groups 2 and 3 each represent useful practical alternatives that are expected to perform on a comparable level, and group 4 as representative for a sub-optimal, but still useful vaccination experience that would be likely to occur in practice.

**Estimand:** The ‘treatment-policy (ITT/effectiveness)’ estimand is considered for the primary objective. The estimand is based on data collected in all randomized BIG subjects regardless of the mother’s possible discontinuation of trial product or treatment adherence.

**Missing data:** imputation is not envisaged, and data will be analysed as collected.

The comparison will be conducted as a series of non-inferiority tests, for each choice of antigen (4) and cut-point (7) with two margins:

- for IgG concentrations: here a GMC ratio of 2/3 is considered adequate.
- for binary endpoints (proportion of subjects with antibody concentrations over prespecified thresholds): 15% points (0.15) on the absolute scale

The null hypothesis for each binary endpoint is:

$$H_0: P_{\text{cut } c, \text{ group } k, \text{ antigen } w} < P_{\text{cut } c, \text{ group } 1, \text{ antigen } w} - 0.15$$
$$k = 2, 3, 4; w = 1, 2, 3, 4; c = 0.1, 0.2, 0.5, 1, 2, 4, 8$$

$P_{\text{cut } c, \text{ group } k, \text{ antigen } w}$  is thus the proportion of subjects with antibody levels above cut-point  $c$ , for vaccination group  $k$  when considering the IgG concentration specific to antigen  $w$ .

The statistical alternative hypothesis is thus:

$$H_1: P_{\text{cut } c, \text{ group } k, \text{ antigen } w} \geq P_{\text{cut } c, \text{ group } 1, \text{ antigen } w} - 0.15$$

If  $H_0$  is rejected this indicates non-inferiority for one specific cut point and antigen.

The evaluation will be done by calculation of the unadjusted risk difference:

$$(P_{c, \text{ group } k, w} - P_{c, \text{ group } 1, w})$$

with a two-sided 90% CI, corresponding to a one-sided test at the 5% significance level. The CI's will be approximative Newcombe-Wilson intervals. The  $H_0$  is rejected if the CI is fully above the -15% point limit, and this therefore corresponds to a one-sided test at a 5% level.

The derivation of the unadjusted risk differences ( $P_{c, \text{ group } k, w} - P_{c, \text{ group } j, w}$ ), with corresponding two-sided 90% CIs, will be derived for all pairs  $1 \leq k, j \leq 4$  and all antigens  $1 \leq w \leq 4$ .

For the observed IgG concentrations, the comparison will be done with the same grouping, but using geometric mean concentrations. Here the  $H_0$  can be expressed as:

$$H_0: \text{GMC}_{\text{group } k, \text{ antigen } w} < 2/3 * \text{GMC}_{\text{group } 1, \text{ antigen } w}$$
$$k = 2, 3, 4; w = 1, 2, 3, 4$$

The evaluation will be done by calculation of the GMCR (GMC ratio) with a two-sided multiplicative 90% CI, again corresponding to a one-sided test at the 5% significance level. The CI's will be based on log-normality. The  $H_0$  is rejected if the CI is fully above the GMCR=2/3 limit and this therefore corresponds to a one-sided test at a 5% level.

The derivation of the GMCRs with corresponding two-sided 90% CIs, will be derived for all pairs  $1 \leq k, j \leq 4$  and all antigens  $1 \leq w \leq 4$ .

As a supplementary analysis, all groups (including placebo) are compared using Analysis of Variance (ANOVA) of the log-transformed values. No adjustment for multiplicity is done.

Due to the large number of performed tests, the non-inferiority procedures are considered of non- confirmatory nature and no control for multiplicity is applied. The expected power of many of the comparisons will be quite low, so only descriptive use of results will be considered.

The primary analyses are based on the BIG analysis set. As sensitivity analyses the primary analyses will be repeated on the BPP analysis set and will be repeated on the BIG set restricted to the babies with an evaluable cord blood sample. A further sensitivity analysis will be done on a further subset of the BPP, eliminating biologically implausible data. Examples of such biological implausible data are (non exhaustive list):

- Data from babies born to mothers with a high concentration of antibodies at delivery, where the baby blood at birth shows no or a very low concentration of antibodies, but who show a high concentration of antibodies at later timepoints
- Data from babies born to mothers with a high concentration of antibodies at delivery, where the baby blood shows no or a very low concentration of IgG antibodies, but where IgG1 is detected at the same timepoints, as part of an exploratory analysis

Setting of the elimination of biologically implausible data will be done after review of the initial immunogenicity data output.

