### 3.5 Primary endpoint(s)

The following primary endpoint(s) will be evaluated, by group:

- Concentrations of IgG antibodies specific to the AlpN proteins in cord blood from each baby:
  - The geometric mean antibody concentrations at birth will be calculated
  - The proportions of babies who achieve a concentration of IgG specific to the AlpN proteins above 0.1, 0.2, 0.5, 1, 2, 4 and 8  $\mu\text{g}/\text{mL}$  at birth will be calculated

The primary immunological endpoint analysis will include the values of these endpoints at the time of delivery, anticipated to be approximately 18 weeks (4  $\frac{1}{2}$  months) from administration of the first dose at 22 weeks GA, or 14 weeks (3 $\frac{1}{2}$  months) from administration of the first dose at 26 weeks GA.

If cord blood cannot be obtained, venous infant blood may be collected within 72 hours of birth.

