**Footnotes**

- a. Gestational age and gender.
- b. Apgar score at 1, 5 and 10 minutes if available (available scores will be collected, 'not recorded' will be an option).
- c. Heart rate (actual, not Apgar score).
- d. Cord blood or infant blood (heel prick or venous sample) within 72 hours of birth.
- e. Heel prick or venous sample.
- f. Age-appropriate developmental milestone check.
- g. After the first 28 days of age, only MAAEs, AEs of special interest (AESI), e.g., GBS disease and abnormal development according to developmental milestones, or SAEs, and CMs prescribed for such events until 180 days of age.
- h. Visit 9-11 may be performed as home visits.

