## VISITS FOR BABIES:

### Visit 8, Delivery:

The following will be undertaken, and results recorded:

Demography, gestational history (gestational age and gender), physical examination\*, head circumference, length, weight, Apgar score (Apgar score at 1, 5 and 10 minutes, available scores will be collected, ‘not recorded’ will be an option), vital signs (heart rate), immunogenicity cord blood sample (or infant blood sample – heel prick or venous, within 72 hours of birth, if cord blood sample not possible, for target blood volumes for babies see Section 4.4), and AE and CM check.

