#### 4.4 Collection and handling of biological samples

The procedures for taking blood samples from the mothers and the babies will follow standard procedures at the investigational sites. The anticipated total amount of blood taken from the mothers during the study period of approximately 5 months until delivery is up to approximately  $10 + 105 + 100 = 215$  mL, please see Table 4, where the total amount of blood taken from the babies will not exceed approximately 20 mL, during their first 3 months of life.

For the babies the target blood volumes for the immunogenicity samples are as follows: 5 mL for cord blood, 2 mL for venous blood and 0.5 mL for heel prick blood. Whenever possible cord blood should be taken, venous blood has second priority followed by heel prick blood.

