## 1.1.2 Endpoints

### 1.1.2.1 Primary endpoints

The following primary endpoint(s) will be evaluated, by vaccination group:

- Concentrations of IgG antibodies specific to the AlpN proteins in cord blood from each baby:
  - The geometric mean (coefficient of variation [CV]) antibody concentrations at birth will be calculated
  - The proportions of babies who achieve a concentration of IgG specific to the AlpN proteins above 0.1, 0.2, 0.5, 1, 2, 4 and 8  $\mu\text{g}/\text{mL}$  at birth will be calculated.

If cord blood cannot be obtained, venous infant blood may be collected within 72 hours of birth and will in that case be considered a valid substitute for the cord blood sample.

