**Footnotes**

- a. Gestational age and gender
- b. Apgar score at 1, 5 and 10 minutes if available (available scores will be collected, 'not recorded' will be an option)
- c. Heart rate (actual, not Apgar score).
- d. Cord blood or infant blood (heel prick or venous sample) within 48 hours of birth.
- e. Heel prick or venous sample.
- f. Age-appropriate developmental milestone check
- g. After the first 28 days of age, only MAAEs, AEs of special interest (AESI), e.g., GBS disease and abnormal development according to developmental milestones, or SAEs, and CMs prescribed for such events until 180 days of age

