### **3.6 Baby Immunogenicity Set (BIG)**

Baby Immunogenicity Set (BIG) contains the babies born to SAF mothers where the baby provides evaluable samples for analysis, either cord or venous blood, within 72 hours of birth. Note that there need not be a 1:1 correspondence between the MIG and BIG.

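### Heel-prick birth samples may be collected, but the primary-endpoint text and the SAP's baby sets leave them out, and the protocol and SAP define BIG differently

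*SAP*

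**What the plan says.** Collection. Protocol Table 3, footnote d, allows at Visit 8: "Cord blood or infant blood (heel prick or venous sample) within 72 hours of birth". The Visit 8 description for babies in Protocol 4.3.2 has the same choice: "heel prick or venous, within 72 hours of birth, if cord blood sample not possible". Protocol 4.4 ranks the specimens: "Whenever possible cord blood should be taken, venous blood has second priority followed by heel prick blood". Its volume targets are 5 mL for cord, 2 mL for venous and 0.5 mL for heel-prick blood. The SAP's own Table 3, footnote d, also names heel prick, with a different window: "Cord blood or infant blood (heel prick or venous sample) within 48 hours of birth".

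Analysis. Protocol 3.5 gives one fallback for the primary endpoint: "If cord blood cannot be obtained, venous infant blood may be collected within 72 hours of birth". SAP 1.1.2.1 repeats this and adds that such a venous sample "will in that case be considered a valid substitute for the cord blood sample". SAP 4.5 states that "a missing or invalid cord blood sample can be replaced by a venous infant blood sample, provided this is taken within 72 hours". None of these three places mentions heel prick.

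Analysis sets. SAP 3.6 limits BIG to babies of SAF mothers where "the baby provides evaluable samples for analysis, either cord or venous blood, within 72 hours of birth". BPP carries the same cord-or-venous condition in Protocol 7.6 and SAP 3.7. Protocol 7.6 defines BIG only through the mother's membership of MIG, with no condition on the baby's specimen. The primary analysis is run on BIG, without imputation.

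**The concern.** A newborn whose only birth sample is a heel prick has been sampled as the protocol permits, yet the analysis text gives that result no route into the primary endpoint. Which set the baby belongs to depends on which document is followed, and the SAP's list of deviations from the protocol (section 7) does not record that BIG was redefined. Because SAP 4.6 also uses BIG for the infant endpoints at 1 and 3 months, the SAP condition reaches visits where both schedules accept heel-prick blood.

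What is at stake is a clear primary population more than precision. Sets are assigned at blinded data review meetings, and the early unblinded analysis through Visit 8 is meant to inform the choice of regimen for phase III (Protocol 2.5). Without a settled rule, eligibility of these babies could be decided case by case.

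**Working it through.** **1. Specimen rules side by side**

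| Place | Cord | Venous | Heel prick |
|---|---|---|---|
| Protocol Table 3 fn d, 4.3.2 Visit 8, 4.4 (collection) | yes | yes | yes |
| SAP Table 3 fn d (collection) | yes | yes | yes |
| Protocol 3.5, SAP 1.1.2.1, SAP 4.5 (primary endpoint) | yes | yes | not named |
| Protocol 7.6 BIG | no specimen rule | no specimen rule | no specimen rule |
| SAP 3.6 BIG | yes | yes | not named |
| Protocol 7.6 BPP, SAP 3.7 BPP | yes | yes | not named |

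The collection texts list heel prick and venous as alternatives, so venous cannot be read as covering both.

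**2. One baby traced through the rules.** Take a mother in MIG, no usable cord or venous sample, and a heel prick inside the window.
- Protocol BIG: in. SAP BIG: out. BPP: out in both documents.
- Primary-endpoint value: none is named in either document.
- A 1-month or 3-month heel-prick sample is permitted by footnote e of both Table 3s. SAP 4.6 analyses it on BIG, so under the SAP the baby is out there too.
- The sensitivity analyses in SAP 4.5 do not bring the baby back. They use BPP, the cord-only part of BIG, or a further subset of BPP.

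**3. The plan's own power figure.** Inputs from SAP 2.3.1, SAP 4.5 and Protocol 7.13: 60 per group, a rate of 95.65% at 1 µg/mL in both groups, margin 0.15, and a two-sided 90% Newcombe-Wilson interval.

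Lower limit = d − √[(p_k − l_k)² + (u_1 − p_1)²], where d = p_k − p_1 and l, u are Wilson limits with z = 1.645. Power is the total binomial probability of outcomes whose lower limit exceeds −0.15. Exact enumeration gives 96.7%.

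Normal approximation: standard error = √(2 × 0.9565 × 0.0435 / 60) = 0.0372. Then 0.15/0.0372 − 1.645 ≈ 2.38, which gives 99.1%.

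The stated figure of above 90% is reproduced.

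**4. Effect of losing heel-prick-only babies.** The documents give no rate, so 5–10% is an assumption. It means 3–6 of 60 babies per group.
- Standard error ratio at 5% loss: √(60/57) = 1.026.
- Standard error ratio at 10% loss: √(60/54) = 1.054.

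| Loss | n per group | Power at 1 µg/mL | Power for Rib-N at 2 µg/mL (rate 82.61%) |
|---|---|---|---|
| 0% | 60 | 96.7% | 70.7% |
| 5% | 57 | 95.8% | 68.4% |
| 10% | 54 | 94.7% | 65.7% |
| 20% | 48 | 92.1% | 62.5% |
| 25% | 45 | 90.0% | 59.3% |

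These are exact Newcombe-Wilson powers, with equal true rates and equal loss in both groups. At 1 µg/mL, power reaches 90% only when a quarter of each group is lost.

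**5. Window.** SAP Table 3, footnote d, says 48 hours. The visit label in the same table and SAP 1.1.2.1, 3.6, 3.7 and 4.5 say 72, as do Protocol 3.5, 4.3.2, 7.6 (BPP) and Table 3. The 48 is an isolated slip.

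**The case against.** The strongest reply is that this is a drafting gap of little consequence. No sentence excludes heel-prick values. Heel prick is the last-choice specimen, Protocol 7.8 expects low attrition, and SAP 4.5 treats the comparisons as non-confirmatory and for descriptive use. Limiting the primary endpoint to cord and venous blood is also defensible: the heel-prick target is 0.5 mL, the ELISAs cover four AlpN and two fusion proteins, and neither document shows capillary blood to be equivalent to cord blood. Acceptance at 1 and 3 months, when no cord sample exists, does not show that equivalence. All of this stands and holds the severity down. It does not remove the conflict between the two BIG definitions or the effect on the later visits.

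A reader might infer three stronger things that the documents do not support.
- **Biased regimen comparison.** If heel-prick-only births were mostly early deliveries, their loss could act differently by regimen, because the last active dose is at 30 weeks in Groups 1 and 3 and at 26 weeks in Groups 2 and 4. But nothing says which births end with a heel prick only. The trial is randomised and observer-blind, and the team collecting blood is separate from the unblinded team.
- **Breach of the treatment-policy estimand.** As written, that estimand concerns the mother's discontinuation and adherence within BIG. It is silent on specimen type.
- **Adequate cover from the cord-only sensitivity analysis.** It removes venous and heel-prick babies together, so it cannot isolate a capillary effect.

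**Conclusion.** The inconsistency is real and minor. Heel prick is a permitted birth specimen in both schedules but is not an accepted primary-endpoint substitute in either document. SAP BIG and both BPP definitions leave it out, while protocol BIG does not. The redefinition of BIG is missing from SAP section 7, and its literal effect extends to the 1- and 3-month analyses.

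The size is unknown and probably small. Under the assumed 5–10% the loss is 3–6 babies per group, with power at 1 µg/mL of 94.7–95.8% against 96.7%. The exclusion follows from omission, so it may be unintended. It would be too strong to say that the plan knowingly discards valid measurements, or that selection has been shown.

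**What to change.** Make these changes before the unblinded Visit 8 analysis:

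1. Align BIG in Protocol 7.6 and SAP 3.6 so that membership does not depend on birth specimen type. This keeps these babies in the 1- and 3-month analyses. The two texts also start from different mothers (MIG and SAF), so settle that in the same edit. List the change in SAP section 7.
2. In Protocol 3.5 and 7.6 (BPP) and SAP 1.1.2.1, 3.7 and 4.5, accept an evaluable heel-prick sample taken within 72 hours of birth when neither cord nor venous blood is available.
3. Report birth samples by specimen type and group. Beside the planned cord-only analysis, add one restricted to cord plus venous samples, so that a capillary effect can be separated.
4. Reconcile the 48 hours in SAP Table 3, footnote d, with the 72 hours used elsewhere.

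Costs: some 0.5 mL samples may not yield all four antigens, and a third specimen type enters the primary set. The protocol wording may need an amendment, and Protocol section 12 requires authority and ethics approval if the change is substantial. If the sponsor prefers to keep heel prick out of the primary endpoint, it should say so with a reason. Items 1 and 4 and the counts in item 3 are still needed.
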